7.0 Criteria for Removal from the Study

- 7.1 Any toxicity that is deemed unacceptable by the study PI.
- 7.2 Disease progression.
- 7.3 Lack of compliance with the requirements of the study.
- 7.4 Withdrawal of consent.
- 7.5 After one year of transplant.

7.6 No matched related or less than 7/8 matched unrelated donor.

8.0 Adverse Events and Reporting Requirements

8.1 AEs during Pacritinib phase

The severity of the adverse events (AEs) will be graded according to the Common Terminology Criteria v4.0 (CTCAE). We will not capture expected Grade 1 and Grade 2 AEs. Grade 3 and 4 AEs will be collected and recorded in the medical record. Only Pacritinib-related adverse events and protocol specific data will be entered into PDMS/CORe. PDMS/CORE will be used as the electronic case report form for this protocol.

Events not included in the CTCAE chart will be scored as follows: General grading:

Grade 2: Moderate: discomfort present with some disruption of daily activity, require treatment.

Grade 3: Severe: discomfort that interrupts normal daily activity, not responding to first line treatment.

Grade 4: Life Threatening: discomfort that represents immediate risk of death

Causality Assessment

For the purpose of this study, events known to be caused by Pacritinib will be assessed as definitely related.

Events known to be caused by components of the transplant package and its direct consequences as well as those events known to be related to drugs used for the treatment of GVHD, infections and supportive treatment will be scored as unrelated.

When the relationship of the adverse event cannot be ruled out with certainty the AE may be considered possibly related.

The PI will be responsible for assessing the causality and will be final arbiter. Documentation of grade, onset/resolution date and attribution will be entered into the patient's medical record and signed by the PI.

Collection of adverse events

Collection of adverse events will reflect the onset and resolution date and maximum grade. Intermittent events should be labeled as such and followed until resolution. If a patient is taken off study while an event still ongoing, this will be followed until resolution unless another therapy is initiated. Pre-existing medical conditions will be recorded only if an exacerbation occurs during the active treatment period. Co-morbid events will not be scored separately.

Adverse events related to Pacritinib will be collected and recorded for the duration of active treatment plus 14 days.

List of expected adverse events related to Pacritinib: Occurring in >10% include:

1. Nausea, vomiting, diarrhea, dehydration

- 2. Anemia, thrombocytopenia
- 3. Fatique

Treatment Duration Definitions:

Active Treatment: patients receiving Pacritinib.

Last day of "Active Treatment": is the last day of Pacritinib.

Reporting Requirement: Serious Adverse Event Reporting (SAE) Language

An adverse event or suspected adverse reaction is considered "serious" if, in the view of either the investigator or the sponsor, it results in any of the following outcomes:

- Death
- A life-threatening adverse drug experience any adverse experience that places the
 patient, in the view of the initial reporter, at immediate risk of death from the adverse
 experience as it occurred. It does not include an adverse experience that, had it occurred in
 a more severe form, might have caused death.
- Inpatient hospitalization or prolongation of existing hospitalization
- A persistent or significant incapacity or substantial disruption of the ability to conduct normal life functions.
- A congenital anomaly/birth defect.

Important medical events that may not result in death, be life-threatening, or require hospitalization may be considered a serious adverse drug experience when, based upon appropriate medical judgment, they may jeopardize the patient or subject and may require medical or surgical intervention to prevent one of the outcomes listed in this definition. Examples of such medical events include allergic bronchospasm requiring intensive treatment in an emergency room or at home, blood dyscrasias or convulsions that do not result in inpatient hospitalization, or the development of drug dependency or drug abuse (21 CFR 312.32).

Important medical events as defined above, may also be considered serious adverse events. Any important medical event can and should be reported as an SAE if deemed appropriate by the Principal Investigator or the IND Sponsor, IND Office.

All events occurring during the conduct of a protocol and meeting the definition of a SAE must be reported to the IRB in accordance with the timeframes and procedures outlined in "The University of Texas M. D. Anderson Cancer Center Institutional Review Board Policy for Investigators on Reporting Unanticipated Adverse Events for Drugs and Devices". Unless stated otherwise in the protocol, all SAEs, expected or unexpected, must be reported to the IND Office, regardless of attribution (within 5 working days of knowledge of the event).

All life-threatening or fatal events, that are unexpected, and related to the study drug, must have a written report submitted within **24 hours** (next working day) of knowledge of the event to the Safety Project Manager in the IND Office.

The investigator will inform CTI Biopharma of any SAE within 24 hours of being aware of the event via email and/or fax.

Unless otherwise noted, the electronic SAE application (eSAE) will be utilized for safety reporting to the IND Office and MDACC IRB.

Serious adverse events will be captured from the time of the first protocol-specific intervention, until 14 days after the last dose of drug, unless the participant withdraws consent. Serious adverse events must be followed until clinical recovery is complete and laboratory tests have returned to baseline, progression of the event has stabilized, or there has been acceptable resolution of the event.

Additionally, any serious adverse events that occur after the 14 day time period that are related to the study treatment must be reported to the IND Office. This may include the development of a secondary malignancy.

Reporting to FDA:

Serious adverse events will be forwarded to FDA by the IND Sponsor (Safety Project Manager IND Office) according to 21 CFR 312.32.

Adverse events known to be related to SOC ALLO TP will not be recorded in PDMS.

List of most common expected adverse events related to SOC ALLO TP:

- 1. Infections in the presence or absence of neutropenia: fungal, bacterial and or viral infections.
- 2. Fever: Non-neutropenic or neutropenic without infection
- 3. Acute graft versus host disease (aGVHD): most commonly manifested by skin rash, diarrhea and abnormal liver function tests could also present with some degree of fever, upper gastrointestinal symptoms (nausea and vomiting) mucositis and eye dryness.
- 4. Gastrointestinal (GI tract): the GI tract manifestations could be not only due
- 5. to direct damage from the preparative regiment but also be a manifestation of GVHD or infections. Therefore, the time course and its presentation are crucial when assessing these as adverse events. Nausea/vomiting, mucositis, diarrhea when presented within first 7 to 10 days most likely will be related to the preparative regimen.
- 6. Skin rash: not related to GVHD could be caused by chemotherapy used for the preparative regimen or antibiotics used a supportive treatment.
- 7. Transaminitis: liver function test elevation.
- 8. Pulmonary events: not related to CHF most likely caused by drug injury or infection. These could present with a pneumonitis pattern manifested with shortness of breath, pulmonary infiltrates on chest radiograph, sometimes accompanied by fever and cough and progress to acute respiratory insufficiency and a diffuse bilateral alveolar pattern.
- 9. Cytokine Storm/ engraftment syndrome: most likely caused by released cytokines.
- 10. Hemorrhagic cystitis: not related to chemotherapy agents used in the proposed preparative regimen is most likely caused by viral infection.
- 11. Thrombotic thrombocytopenic purpura (TTP).
- 12. Veno-occlusive Disease of the Liver (VOD): could be caused by Busulfan. Some antimicrobial agents have been also incriminated in its development.
- 13. Fluid overload due to hydration required for conditioning regimen, blood product transfusions and or IV alimentation
- 14. Graft failure.
- 15. Chronic GVHD.

- 16. For the purpose of this study, the following events would not be considered adverse events and would not be recorded in the database:
 - a. Flu-like symptoms not associated with infection
 - b. Abnormal laboratory findings considered associated to the original disease
 - c. Isolated changes in laboratory parameters such as electrolyte, magnesium and metabolic imbalances, uric acid changes, elevations of ALT, AST, LDH and alkaline phosphatase.

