Pacritinib, a Jak2/Flt 3 inhibitor, has activity in myeloid and lymphoid malignancies. Currently it is in Phase 3 studies in patients with myelofibrosis. Details of this molecule are in the attached investigator brochure and a brief summary follows. It is a potent selective inhibitor of mutant as well as normal Jak2 kinase. Preclinical studies showed its activity in suppressing Jak 2 mediated tumors. PK studies in clinical trials showed slow absorption (Tmax 4-6 hours) and dose related increase in systemic exposure up to 400 mg per day. Terminal elimination half-life was 47 hours. Food did not impair absorption. At 100 mg/day dose steady state levels exceeded IC50 values for inhibition of Jak2/Flt3 kinase. Phase I studies identified 400 mg daily as dose for further studies. Dose limiting toxicity included grade 3 QTc prolongation, grade 3 diarrhea and grade 2 dizziness and blurred vision. Most common adverse events occurring in more than 20% were diarrhea, nausea, vomiting, constipation, dyspnea, fatigue and edema. Most events were mild to moderate severity. Only grade 3 or higher adverse event occurring in more than 10% of patients were anemia or thrombocytopenia (16%). MRI showed ≥ 25% spleen volume reduction in 55% of patients. An improvement in all symptoms relevant to myelofibrosis was seen. Thus, Pacritinib is very safe and highly effective therapy for patients with myelofibrosis and we would like study its role pre-transplant to improve transplant outcomes.

Correlative Research Studies (optional):

To evaluate the effect of the JAK2 inhibitor Pacritinib on immune recovery and graft-versus-host disease post-transplant

Janus kinase-2 (JAK2) conveys receptor-binding signals by several inflammatory cytokines, via phosphorylation of STAT3. Selective inhibition of JAK2 was shown to induce tolerance to allo-antigens, while preserving de novo responses to pathogens 48. Selective JAK2 inhibition was also shown to preserve Treg numbers through preservation of the IL-15/JAK3/pSTAT5 pathway.

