CTCAE Toxicity Grade	Management/ Action	
1 or 2	No change.	
3	 Hold treatment. If the toxicity resolves to grade ≤ 1 or to the baseline grade within 7 days, treatment may be resumed at the same level or the next lower dose, at the discretion of the investigator after discussion with the sponsor. Toxicity that does not resolve to grade ≤ 1 or to the baseline grade within 7 days requires dose reduction to the next lower dose level. 	
4	 Hold treatment. If the toxicity resolves to grade ≤ 1 or to the baseline grade within 7 days, treatment may be resumed, but dose will be reduced by one dose level from the level at which the toxicity was observed. If grade 4 toxicity occurs at the lowest dose of 200 mg/day, the patient should be discontinued from the study. 	

4.3.6 The lowest dose of pacritinib used in the study will be 200 mg/day. If toxicity persists despite dose reduction to 200 mg/day, the patient should be discontinued from treatment.

4.4 Dose Management Guidelines for Hematologic Toxicities:

- 4.4.1 Myelosuppression is an expected event in patients with MF. However, myelosuppression with associated complications such as fever, infection, or bleeding or myelosuppression that worsens during treatment (based on local laboratory values) must be reported as an AE.
- 4.4.2 Patients with myelosuppression may receive supportive care including transient use of granulocyte colony stimulating factor for the treatment of febrile neutropenia and transfusion as clinically indicated.
- 4.4.3 Patients receiving pacritinib are not allowed to receive hematopoietic growth factors such as erythropoietin for the treatment of anemia.
- 4.4.4 Patients with clinically significant worsening of myelosuppression (as judged by the investigator and based on local laboratory values) for more than 7 days or myelosuppression associated with infection or bleeding should have pacritinib dosing interrupted. Pacritinib may be restarted at a reduced dose once the toxicity has resolved to grade ≤ 2 or to the baseline grade and the complications of myelosuppression such as infection or hemorrhage have resolved.

4.5 Allogeneic graft:

Peripheral blood (PB) or bone marrow (BM) progenitor cells may be used in this study peripheral blood will be preferred.

4.6 **Preparative Regimen**:

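### Section 8.1 leaves out expected grade 1-2 adverse events, which conflicts with Section 4.4.1 on worsening myelosuppression and relies on an open, incomplete list, so the planned adverse event rates cannot be read as any-grade incidence

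*Combined protocol and SAP*

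**What the plan says.** Section 8.1 sets the capture rule for the pacritinib phase: "We will not capture expected Grade 1 and Grade 2 AEs". For higher grades it says "Grade 3 and 4 AEs will be collected and recorded in the medical record". A separate attribution filter applies to the electronic case report form: "Only Pacritinib-related adverse events and protocol specific data will be entered into PDMS/CORe".

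The expected events are introduced by "List of expected adverse events related to Pacritinib: Occurring in >10% include". The items are nausea, vomiting, diarrhea, dehydration, anemia, thrombocytopenia and fatigue.

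Three other places bear on this:

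- Section 4.4.1, on hematologic toxicity, says that "myelosuppression that worsens during treatment (based on local laboratory values) must be reported as an AE". No grade threshold is attached.
- Section 2.0, in the account of pacritinib, says "Most common adverse events occurring in more than 20% were diarrhea, nausea, vomiting, constipation, dyspnea, fatigue and edema", and then "Most events were mild to moderate severity". It adds that the only grade 3 or higher event above 10% was anemia or thrombocytopenia, at 16%.
- Section 9.4 describes constipation as reported to be related to pacritinib and peripheral edema as commonly reported. Neither is on the 8.1 list.

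Section 6.0, under Secondary Analyses, plans a descriptive table of adverse event rates in patients transplanted from an eligible donor, and a separate summary for those who take pacritinib but are not transplanted. Neither is described as limited to particular grades.

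**The concern.** The expected list decides which low-grade events exist in the data, so it needs to be complete and consistent with the rest of the protocol. It falls short in two ways.

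First, anemia and thrombocytopenia are listed as expected, so 8.1 says that a grade 1 or 2 occurrence is not captured. Section 4.4.1 says that the same occurrence must be reported if it represents worsening on treatment. Staff facing a new grade 2 thrombocytopenia have two opposite instructions, and different patients may be handled differently.

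Second, the word *include* leaves the list open, and events described elsewhere as common are missing from it. Whether grade 1-2 constipation or edema is kept depends on whether the person recording it regards it as expected.

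At stake is the meaning of the safety table. Pacritinib is proposed as a well-tolerated pre-transplant agent, and Section 2.0 says that most of its adverse events were mild to moderate. A table of rates with no grade label, built under this rule, would be missing much of that low-grade burden without saying so. Low grade is not the same as unimportant here: Section 2.0 counts grade 2 dizziness and blurred vision among the dose-limiting toxicities.

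**Working it through.** The plan gives no figure of its own for adverse event capture, so there is none to reproduce. The numbers below come from Section 2.0. The denominators come from Section 6.0: 21 evaluable patients, and up to 40 enrolled in all.

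**1. The two rules for low-grade cytopenias**

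| Event on pacritinib | Section 8.1 | Section 4.4.1 |
|---|---|---|
| Worsening anemia or thrombocytopenia, grade 1-2 | Not captured (expected) | Must be reported |
| Worsening anemia or thrombocytopenia, grade 3-4 | Collected | Must be reported |

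The conflict is confined to the first row.

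**2. Size of the understatement for listed non-hematologic events**

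Let p be the share of patients with the event at any grade and g the share with it at grade 3 or higher. Under 8.1 only g is recorded, so the share of affected patients lost is 1 − g/p.

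For diarrhea, nausea, vomiting and fatigue, Section 2.0 gives p > 0.20. Because only anemia or thrombocytopenia exceeded 10% at grade 3 or higher, g ≤ 0.10 for these four. Hence

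1 − g/p ≥ 1 − 0.10/0.20 = 0.50.

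Expected counts at those bounds:

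- 21 patients: 0.20 × 21 = 4.2 affected, 0.10 × 21 = 2.1 recorded.
- 40 patients: 0.20 × 40 = 8.0 affected, 0.10 × 40 = 4.0 recorded.

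These are expectations, not ceilings. With a true grade 3+ rate of 10% in 21 patients, the chance of recording three or more is about 35% (1 − 0.109 − 0.255 − 0.284 = 0.352).

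The documents do not give exact rates. Over an assumed range, the share lost is:

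| Any grade p | g = 2% | g = 5% | g = 10% |
|---|---|---|---|
| 20% | 90% | 75% | 50% |
| 40% | 95% | 87.5% | 75% |
| 60% | 96.7% | 91.7% | 83.3% |
| 80% | 97.5% | 93.8% | 87.5% |

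The same calculation cannot be made for anemia and thrombocytopenia, because Section 2.0 gives no any-grade rate for them.

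**3. Could an unlisted event appear more common than a listed one?**

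This needs two assumptions: the list is read as closed, and the unlisted event is judged related to pacritinib. An unlisted event such as constipation is then recorded at all grades (taken as 20%), and diarrhea only at grade 3 or higher. With independent binomial counts C and D, P(C > D) = Σ P(C = c) P(D < c):

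| Listed event, grade 3+ rate | 21 patients | 40 patients |
|---|---|---|
| 10% | 0.76 (tie 0.12) | 0.87 (tie 0.06) |
| 5% | 0.90 | 0.98 |
| 16% (anemia or thrombocytopenia) | 0.55 | 0.63 |

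If the list is read as open, the unlisted events may also be dropped at grade 1-2 and this ordering need not arise.

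**The case against.** The strongest reply is that selective collection of low-grade events is a legitimate choice in a small phase II study of a drug with a known profile. Grade 3-4 events are kept, including the only kind that exceeded 10% at that level. All serious adverse events go to the IND Office whatever their attribution. Adverse event rates are not among the numbered items by which Section 1.0 evaluates safety and efficacy, and the table is descriptive. Section 4.4.1 first calls myelosuppression expected and then singles out worsening, so it can be read as an exception to 8.1. A table labeled as grade 3 or higher for expected events would be valid with no further data.

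Much of this stands. Capturing every low grade is partly a preference, and the exception reading of 4.4.1 is reasonable. But 8.1 does not state the exception, the list is not closed, and the table carries no grade label. The choice is defensible only once those three things are in place.

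A reader might also infer more than the documents support:

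- *That the list contradicts the protocol's own frequencies.* It does not. It covers related events and is worded as open, while the Section 2.0 rates are not restricted to related events. Dyspnea, also above 20% there, is not named in Section 9.4. The list is incomplete, which is a weaker statement.
- *That the table will misrank toxicities.* This needs a closed list and attribution to pacritinib. Section 2.0 also puts all seven events in one group above 20%, so the true order is not known.
- *That tolerability could not be checked at all.* Grade 3-4 events remain, and blood counts are scheduled throughout treatment. Whether pacritinib is less myelosuppressive than ruxolitinib is a comparison that this single-arm trial cannot test at any grade.

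**Conclusion.** The point holds in limited form. Sections 8.1 and 4.4.1 give opposite instructions for worsening grade 1-2 anemia and thrombocytopenia and must be reconciled. The expected list is open and incomplete against Sections 2.0 and 9.4, so retention of low-grade events is inconsistent.

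If the Section 6.0 table is read as any-grade incidence, the rates for diarrhea, nausea, vomiting and fatigue would be understated by about half or more in expectation, and by 50% to 97.5% over the range examined. This assumes that the Section 2.0 rates carry over to this trial and that the related events which reach the case report form have a similar grade mix. Those rates are all-cause, and the documents do not give the grade mix for related events.

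Misranking is a possibility under one reading of the list, not an established consequence. The capture of grade 3-4 events and serious adverse events is unaffected by this rule. The correction is worth making because it is cheap, and low-grade symptoms not recorded at the time cannot be reliably recovered later.

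**What to change.** 1. State in 8.1 that worsening myelosuppression under 4.4.1 is recorded whatever its grade, so that the two sections agree.
2. Make the expected list complete against Sections 2.0 and 9.4, and closed, so that expected has one meaning.
3. Report hematologic toxicity as grade-shift tables from the blood counts that Sections 5.1 and 5.2 already schedule at baseline, day 14 of cycle 1 and monthly on pacritinib.
4. For other drug-phase events, do one of two things. Either apply a single grade floor to all events, listed or not, or keep selective capture and label the Section 6.0 table as grade 3 or higher for expected events. A floor at grade 2 would lose unexpected grade 1 events that 8.1 does not now exclude; recording all grades avoids that.

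The cost is some extra data entry and analysis for at most 40 patients, lasting longer for those who continue pacritinib without transplant under 4.1.4. No new tests or visits are needed. Labeling alone would cost almost nothing, but would leave low-grade rates for the expected events unknown.

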We will use descriptive statistical methods to tabulate safety parameters such as the rate of adverse events. Only patients who undergo transplant with a matched related or at least 7/8 matched unrelated donor will be include in these analyses.

We will separately summarize safety and other data for patients who receive pacritinib but who do not undergo stem cell transplant.

We will perform a descriptive statistical analysis of the Participant Follow-up Assessment questionnaire (Global Impression of Change Scale, Appendix F.) data collected at approximately 1, 3, 6, and 12 months post-transplant.

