9.4 Observed Risks

The adverse effects observed in toxicity studies, as well as data from phase 1 and 2 clinical studies in patients with advanced MF, AML, and lymphoma:

- Hematologic: Reversible myelosuppression; leukopenia, neutropenia, thrombocytopenia, and anemia have been observed; these events are common in hematologic malignancies and may not be related to pacritinib administration. Thrombocytopenia, anemia, neutropenia, and leukopenia ADRs were more common in lymphoid than myeloid patients. Patients participating in clinical trials of pacritinib will be monitored frequently for myelosuppression. Provisions for interruption of treatment and dose reduction in the event of myelosuppression are outlined in clinical trial protocols.
- Gastrointestinal: Treatment with pacritinib is associated with dose-related diarrhea and nausea. Vomiting, abdominal pain, abdominal distension, anorexia, and constipation have also been reported to be related to pacritinib administration. Diarrhea and vomiting ADRs were more common in myeloid studies than lymphoid studies, but the reverse was true for constipation. Nausea was the same in both populations. Antiemetic and antidiarrheal medications should be prescribed prophylactically to control symptoms. Fluid and electrolytes should be replaced as needed to prevent dehydration. Pre-existing nausea, vomiting, and diarrhea should be adequately controlled before beginning therapy. Patients

- with significant GI symptoms despite optimal supportive care may have study drug interrupted or have the dose of study drug reduced per protocol.

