- Cardiac: QTc prolongation has been reported in association with pacritinib therapy. A post-hoc review of the patients in the phase 1-2 Studies SB1518-2007-001 and SB1518-2008-003 identified 9 patients with at least one reported QTc exceeding 500 ms; all but one were treated at a pacritinib dose of ≥ 400 mg QD. Therapy was continued in most of these patients for extended periods of time after the observations of QTc prolongation. In addition, pre-study cardiac history was noted in 7 patients, and 8 patients were taking concomitant medications associated with QTc prolonga-tion. Other cardiac TEAEs and ADRs were rare in all pacritinib-treated populations. Based on these observations, investigators are advised to exclude any patient with a baseline QTc > 450 ms and to perform routine ECG monitoring during treatment. For patients with identified changes in treatment-emergent ECG abnormalities or other cardiac events, study drug may be interrupted or the dose may be reduced per protocol.
- Hepatic: Animal studies suggest that pacritinib treatment may cause dose-related hepatotoxicity. There has been little evidence of hepatotoxicity in clinical trials to date. Significant increases in aminotransferases have been observed infrequently and have not been accompanied by concomitant increases in bilirubin. Most reported hepatic toxicities were seen in the myeloid population. No instances of hepatic dysfunction meeting Hy's Law criteria have been observed. Hepatic function (AST/SGPT, ALT/SGOT, alkaline phosphatase, and total bilirubin) will continue to be assessed at frequent intervals during treatment with pacritinib.
- **Renal**: Animal studies suggest that treatment may cause dose-related renal toxicity. To date, little impact on renal function has been observed in human clinical trials. Assessment of renal function (creatinine, BUN, sodium, potassium) will be undertaken frequently in patients participating in clinical trials of pacritinib.

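### Only adverse events judged pacritinib-related enter the case report form, and the causality rules conflict for dual-cause events, so non-serious grade 3 or higher events can be missing from the reported rates

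*Combined protocol and SAP*

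**What the plan says.** Section 8.1 (AEs during Pacritinib phase) sends grade 3 and 4 events to the medical record, but "Only Pacritinib-related adverse events and protocol specific data will be entered into PDMS/CORe". It adds that "PDMS/CORE will be used as the electronic case report form for this protocol".

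The Causality Assessment paragraph of the same section has three rules:

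- "events known to be caused by Pacritinib will be assessed as" definitely related.
- Events caused by the transplant package, and "those events known to be related to drugs used for the treatment of GVHD, infections and supportive treatment will be scored as" unrelated.
- An event whose relationship cannot be excluded with certainty *may* be scored possibly related.

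On who decides: "The PI will be responsible for assessing the causality and will be final arbiter". No independent adjudication is described.

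Section 6.0 (Secondary Analyses) plans the safety report: "We will use descriptive statistical methods to tabulate safety parameters such as the rate of adverse events". It restricts this to patients transplanted from a matched related or at least 7/8 matched unrelated donor. Patients who take pacritinib but are not transplanted are summarised separately.

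**The concern.** Relatedness acts here as a filter before data entry, not as a variable to be analysed. The tabulated rates are a subset of what happened, selected by one assessor's attribution. In a single-arm trial there is no control rate against which that attribution can be checked.

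The first two causality rules work by type of event. An event can be a known effect of pacritinib and also a known effect of an anti-infective or supportive drug. Both rules then apply, with opposite results, and the text does not say which prevails. The third rule could resolve such cases but is only permissive.

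At stake is the safety half of the secondary objectives, specifically the rates of non-serious grade 3 or higher events during the pacritinib phase. The progression-free survival endpoint is not affected.

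**Working it through.** The plan states no figure for this point, so there is nothing to reproduce. The check sets the sections side by side and ends with an illustration.

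**1. Source of the rates.** Section 6.0 tabulates adverse event rates without naming a source. Section 8.1 names PDMS/CORe as the electronic case report form, and no other adverse event data source is named. An event kept out of PDMS/CORe is therefore absent from the rates unless someone returns to the charts.

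**2. Where the rules can collide.** Pacritinib stops 21 days before conditioning (Section 4.1.3). Routine collection ends 14 days after the last dose (Section 8.1). The gap is 21 − 14 = 7 days, so collection closes about a week before conditioning, and the transplant-package part of the *unrelated* rule hardly matters. The live overlap is with infection and supportive drugs given during pacritinib. Such drugs are expected: Section 9.4 advises prophylactic antiemetics and antidiarrheals.

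**3. Which events are exposed.** Section 8.1 lists as expected and related to pacritinib: nausea, vomiting, diarrhea, dehydration, anemia, thrombocytopenia and fatigue. That list supports a *definitely related* score for them. QTc prolongation is not on it, although Section 2 (Pacritinib) reports grade 3 QTc prolongation as dose-limiting. Section 9.4 shows that a second possible cause is common: of 9 patients in earlier studies with a QTc above 500 ms, "8 patients were taking concomitant medications associated with QTc" prolongation.

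**4. Cytopenias.** Section 4.4.1 requires myelosuppression that worsens on treatment, or has complications, to be reported as an adverse event. Item 16b, at the end of the Section 8.0 list of transplant-related events, says that laboratory abnormalities considered associated with the original disease are not adverse events and are not recorded in the database. Although it sits in a transplant list, item 16 is introduced as applying to the study. A worsening cytopenia attributed to myelofibrosis falls under both provisions, again without precedence.

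**5. Can an *unrelated* score be re-checked?** Section 5.2 says that no data will be captured on supportive medications or their side effects. The case report form therefore holds neither the excluded event nor the drug blamed for it. Grade, dates and attribution are in the signed chart, so chart review is the only route.

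**6. Illustration.** Inputs: a true grade 3 or higher rate of 16% (the anemia or thrombocytopenia figure in Section 2, used as a stand-in); n = 21, the minimum evaluable number in Section 6.0; and f, the share scored unrelated, which is an assumption and not in the documents.

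Recorded rate p = 0.16 × (1 − f); expected recorded events = 21 × p; P(at least one recorded) = 1 − (1 − p)^21.

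| f (assumed) | recorded rate | expected events | P(at least one) |
|---|---|---|---|
| 0 | 16% | 3.36 | 0.97 |
| 0.25 | 12% | 2.52 | 0.93 |
| 0.50 | 8% | 1.68 | 0.83 |
| 0.75 | 4% | 0.84 | 0.58 |
| 1 | 0% | 0 | 0 |

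With so few expected events, reclassifying one or two changes the reported rate materially.

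**The case against.** The case on the other side is substantial, and much of it stands.

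- **The plan pre-labels most signature toxicities as related.** The gastrointestinal events, anemia, thrombocytopenia and fatigue are on the Section 8.1 list. A reader might infer that the *unrelated* rule strips these events from the database. The documents do not support that: the *definitely related* rule applies to them at least as directly. Section 9.4 does say of cytopenias that "these events are common in hematologic malignancies and may not be related to pacritinib administration", but that is background risk information, not an attribution rule.
- **Serious events are protected.** Section 8.0 requires all serious events to go to the IND Office whatever their attribution. This limits the exposure to non-serious events, but does not place those in the case report form.
- **The loss is reversible.** Grade 3 and 4 events stay in the chart, and monthly blood counts, chemistry and EKGs are scheduled (Section 5.2). Some of these results might count as protocol-specific data. The documents do not say so, and an EKG value is not a graded adverse event. It would be wrong to say that the loss cannot be undone, but undoing it needs a chart review that the plan does not provide for.
- **The direction of bias is not fixed.** Scoring known pacritinib effects as related by type could inflate the related rate. Against the truly drug-caused rate, the sign is indeed unknown. Against the all-cause rate, a filter can only remove events.
- **The QTc figure does not measure loss.** A reader might take 8/9 = 89% as the share of QTc events that would vanish. Those patients come from earlier studies, were identified after the fact and have no denominator. The drug class is not given, so the medications need not be infection or supportive drugs. This trial also excludes a baseline QTc above 450 ms.
- **No pooled rate over 40 patients is planned.** Forty is the enrolment ceiling; Section 6.0 tabulates the transplanted evaluable patients and summarises the rest separately.

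**Conclusion.** The concern holds in a limited form. The case report form admits only events that the investigator judges related to pacritinib. The causality rules give opposite answers for an event with two known causes, and the option that would keep such events is not mandatory. Section 5.2 removes the data needed to re-check the judgement. Non-serious grade 3 or higher events with a plausible second cause can therefore be missing from the reported rates. QTc prolongation is the most exposed, being dose-limiting but absent from the list of expected related events. Cytopenias attributed to the disease are exposed through item 16b.

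The loss is discretionary, not prescribed, and chart review could recover it. Its size cannot be estimated from the documents. The fall from 16% to 8% in 21 patients rests wholly on the assumption that half the events are scored unrelated, and the possible range runs from 16% (none) to 0% (all). The point also assumes that the Section 6.0 rates will be drawn from PDMS/CORe, which is the natural reading but is not stated outright. The plan should be changed because the remedy is cheap; the documents do not show that the reported rates will be wrong.

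**What to change.** - **Section 8.1, data entry:** enter every grade 3 or higher adverse event with onset from first dose to 14 days after the last dose in PDMS/CORe, whatever its attribution, with attribution as a recorded field.
- **Section 6.0:** tabulate all-cause and pacritinib-related rates side by side, and name PDMS/CORe as the source.
- **Section 8.1, Causality Assessment:** state that an event that is also a known pacritinib effect is not automatically scored *unrelated*, and is scored at least *possibly related* when a pacritinib contribution cannot be ruled out.
- **Section 8.0 item 16b and Section 4.4.1:** reconcile the two so that worsening grade 3 or higher cytopenias on pacritinib are entered.

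The cost is a few sentences of amended text and modest extra data entry, since grade, dates and attribution are already documented and signed in the chart. Reported rates will look somewhat less favourable. The all-cause table will include some events not caused by the drug, which is why the related rate should stand beside it.
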